9.1 Missing or Inconclusive Data Handling

In general there will be no imputation of missing data other than for partial or missing dates. Partial start and end dates for medical history, concomitant medications, and AEs will be imputed as outlined in [Appendix 1](#). Completely missing dates will only be imputed for AEs.

The original dates will be displayed in data listings along with the relative study day for complete dates. imputed dates will be used in derivations only (e.g., to determine treatment-emergence status, etc.).

9.2 Definition of Baseline

Baseline measures are defined as the last measure prior to the initiation of study treatment, usually at Visit 2 (Day 1). For assessments that are not performed at Visit 2 (i.e. FP and FA), the screening Visit 1 measures will be considered as baseline.

9.3 Visit Windows and Visit Mapping

The following table lists the scheduled visits and planned study day along with the corresponding visit window that will be used to map visits occurring outside of the scheduled times.

Scheduled Visit	Planned Study Day	Visit Window
Visit 1 / Screening	Day -7*	<= Day -1
Visit 2	Day 1	Day 1
Visit 3	Day 8	Day 2 to Day 11
Visit 4	Day 15	Day 12 to Day 18
Visit 5	Day 22	Day 19 to Day 25
Visit 6	Day 29	Day 26 to Day 32
Visit 7	Day 36	Day 33 to Day 39
Visit 8 / End of Treatment (EOT)	Day 43	Day 40 to Day 46
Visit 9 / Follow-Up (FU)	Day 50	Day 47 to Day 53
Visit 10 / FU	Day 57	Day 54 to Day 60
Phone / FU	Day 71	>=Day 61

* Visit 1/Screening of Fundus Photography/FA can be performed up to Day -14, per the protocol.

Summary tables will be presented by scheduled visit using the following algorithm. If there are multiple non-missing assessments within a visit window, then the visit closest to the scheduled visit will be used. If multiple visits are equidistant from the scheduled visit, then the scheduled visit and unscheduled visit

will be selected in that order. If multiple visits of the same type are equidistant from the scheduled window, then the earliest visit of that type will be selected.

Subject listings will include all visits.

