17.1.2.6 Observation/Repeat Testing

- Initiate close observation of subjects by repeat testing of ALT, AST, and total bilirubin (with fractionation by total and direct) at least weekly until the laboratory ALT and/or AST abnormalities stabilize or return to normal, then according to the protocol. Depending on further laboratory changes, additional parameters identified e.g. by reflex testing will be followed up based on medical judgment and GCP.

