16.4 Clinical Laboratory Values

Blood samples and urine must be collected at every visit. Safety laboratory examinations will include hematology, biochemistry, coagulation, and qualitative urine analysis.

- Serology (screening only): hepatitis A (anti-immunoglobulin M (IgM), anti-IgM)), hepatitis B (hepatitis B antigen, anti-HBs, DNA), hepatitis C (anti-hepatitis C virus (HCV), ribonucleic acid (RNA) if anti-HCV positive), hepatitis D (anti-IgM, anti-immunoglobulin G (IgG)), hepatitis E (anti-hepatitis E virus (HEV), anti-HEV IgM, RNA if anti-HEV IgM positive), anti-smooth muscle antibody (titer), anti-nuclear antibody (titer), anti-liver-kidney microsomes (LKM) antibody, antimitochondrial antibody, Epstein Barr virus (vascularized composite allotransplantation (VCA) IgG, VCA IgM), cytomegalovirus (IgG, IgM), herpes simplex virus (IgG, IgM), varicella (IgG, IgM), parvovirus (IgG, IgM), toxoplasmosis (IgG, IgM)
- Hematology: hemoglobin, red blood cell count (RBC), white blood cell count (WBC) with differential, platelets
- Biochemistry: glucose, sodium, potassium, calcium, inorganic phosphate, creatinine, aspartate aminotransferase (AST), alanine aminotransferase (ALT), alkaline phosphatase (AP), lactate dehydrogenase (LDH), total bilirubin (if elevated provide direct bilirubin), urea, total protein, albumin, uric acid

- Coagulation: activated partial thromboplastic time (aPTT), prothrombin time (PT)/international normalized ratio (INR)
- Urine: potential of hydrogen (pH), glucose, erythrocytes, leukocytes, protein, nitrite and glomerular filtration rate (GFR)

All safety laboratory measurements will be performed at all scheduled visits by a central laboratory (except serology which is evaluated at screening only) . Investigators will get guidance and instructions on laboratory sampling and processing through a separate Lab Manual provided by the central laboratory.

The investigator is responsible for determining and documenting if out of range laboratory values are clinically significant or not. All clinically significant values will be recorded as AEs in the eCRF and followed until resolution. Once resolved, the AE eCRF page(s) will be updated.

Continuous biochemistry, hematology, and coagulation assessments will be summarized by visit and changes from baseline using quantitative summary statistics. The data for biochemistry and hematology will also be presented in listings.

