14.3.8.2.3	Shift in Slit Lamp Biomicroscopy Hypopyon and Retinal Tear and Detachment	Safety Set
14.3.8.2.4	Shift in Slit Lamp Biomicroscopy Lens Status	Safety Set
14.3.8.2.5	Shift in Slit Lamp Biomicroscopy Lens Opacity for Phakic Eyes	Safety Set
14.3.9	Summary of Intraocular Pressure	Safety Set
14.3.10.1.1	Summary of Clinical Laboratory Values - Biochemistry	Safety Set
14.3.10.1.2	Shift in Clinical Laboratory Values - Biochemistry	Safety Set
14.3.10.2.1	Summary of Clinical Laboratory Values - Coagulation	Safety Set
14.3.10.2.2	Shift in Clinical Laboratory Values - Coagulation	Safety Set
14.3.10.3.1	Summary of Clinical Laboratory Values - Hematology	Safety Set
14.3.10.3.2	Shift in Clinical Laboratory Values - Hematology	Safety Set
14.3.11	Summary of Vital Signs	Safety Set
14.3.12.1	Summary of Electrocardiogram Overall Results	Safety Set
14.3.12.2	Shift in Electrocardiogram Overall Results	Safety Set

25. Listings

Listing Number	Title	Set
16.2.1	Subject Disposition	ITT Set
16.2.2	Protocol Deviations	ITT Set

Listing Number	Title	Set
16.2.3.1	Inclusion and Exclusion Criteria	All Patients
16.2.3.2	Subjects Excluded from Analysis Sets	ITT Set
16.2.3.3	Informed Consent	ITT Set
16.2.4.1	Demographics	ITT Set
16.2.4.2	Ocular Medical History	ITT Set
16.2.4.3	Non-Ocular Medical History	ITT Set
16.2.4.4	Prior and Concomitant Ocular Medications	ITT Set
16.2.4.5	Prior and Concomitant Non-Ocular Medications	ITT Set
16.2.5.1	Study Drug Administration	ITT Set
16.2.6.1	Best Corrected Visual Acuity Scores (ETDRS)	ITT Set
16.2.6.2	Spectral Domain – Optical Coherence Tomography	ITT Set
16.2.6.3	Fundus Photography	ITT Set
16.2.6.4	Fluorescein Angiography	ITT Set
16.2.7.1	All Adverse Events	ITT Set
16.2.7.2	Serious Adverse Events	ITT Set
16.2.7.3	Adverse Events of Special Interest	ITT Set
16.2.7.4	Adverse Events Leading to Subject Withdrawal	ITT Set
16.2.7.5	Deaths	ITT Set
16.2.8.1	Slit-Lamp Biomicroscopy	ITT Set
16.2.8.2	Intraocular Pressure	ITT Set
16.2.8.3	Vital Signs	ITT Set
16.2.8.4	Physical Examination	ITT Set
16.2.8.5	Biochemistry	ITT Set
16.2.8.6	Hematology	ITT Set
16.2.8.7	Coagulation	ITT Set
16.2.8.8	Urine Analysis	ITT Set
16.2.8.9	Serology	ITT Set
16.2.8.10	Electrocardiogram	ITT Set

26. Figures

Figure Number	Title	Set
14.2.1	By-Visit Box Plot Summary of BCVA Letter Score in the Study Eye	Evaluable Set
14.2.2	By-Visit Box Plot Summary of Central Subfield Thickness (μm) in the Study Eye as Measured by SD-OCT	Evaluable Set

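### By default, an unscheduled peak laboratory value that is judged not clinically significant and misses the combined hepatic AESI definition appears in listings but in no laboratory summary or shift table

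*SAP*

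**What the plan says.** **Selection rule.** SAP 9.3 states its scope as "Summary tables will be presented by scheduled visit using the following algorithm". Where a window holds several results, "If there are multiple non-missing assessments within a visit window, then the visit closest to the scheduled visit will be used". For ties, "If multiple visits are equidistant from the scheduled visit, then the scheduled visit and unscheduled visit" are taken in that order. A typical window is Visit 4, "Day 12 to Day 18", around a planned Day 15. Visit 3 is wider, from Day 2 to Day 11. The section ends with "Subject listings will include all visits".

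**Laboratory tables.** SAP 16.4 says "Continuous biochemistry, hematology, and coagulation assessments will be summarized by visit and changes from baseline using quantitative summary statistics". It does not mention shift tables. These appear only in the SAP Section 24 table list, for example Table 14.3.10.1.2, "Shift in Clinical Laboratory Values - Biochemistry", with counterparts for coagulation (14.3.10.2.2) and hematology (14.3.10.3.2). No listed table uses the worst value, any value after baseline, or a threshold.

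**Other routes into the tables.** Under SAP 16.4 and Protocol 7.2.2, values that the investigator considers clinically significant are recorded as AEs. Protocol 7.2.1.2.3 asks for the highest grade reached, and Tables 14.3.7.1 and 14.3.7.2 present maximum severity. The hepatic AESI in SAP 16.1 applies to subjects with normal liver function at baseline. It needs AST and/or ALT at least 3 times ULN together with total bilirubin at least 2 times ULN in the same sample. AESIs are tabulated in Table 14.3.5.

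**The concern.** Selecting by date suits by-visit means, because it gives each subject one value per visit. It suits laboratory safety less well. The question there is how far any subject moved out of range, and the draw that answers it may be an unscheduled one.

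Change from baseline in laboratory values is a listed safety endpoint in Protocol 10.4.2 and SAP 16. The trial has one arm and about 30 subjects, so a reader of the tables would want any marked abnormality counted. A transaminase peak found between visits, not judged clinically significant and without the bilirubin rise, would be left to the listings, which give no count or percentage. The minimum and maximum required by SAP 9.4 do not recover it, because in a by-visit table they are taken over the selected values.

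**Working it through.** The plan gives no figure to reproduce. The check is on how the selection rule behaves and which routes remain.

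**Inputs**
- Planned days p for Visits 3 to 10: 8, 15, 22, 29, 36, 43, 50, 57 (SAP 9.3).
- Each of these windows ends at p + 3 (SAP 9.3; for example Day 11 for Visit 3 and Day 18 for Visit 4).
- Scheduled draw s on p − 1, p or p + 1 (schedule of events, ±1 day).
- Laboratory tests are scheduled at every one of these visits.

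**Rule.** An unscheduled draw on day u replaces the scheduled one only if |u − p| < |s − p|. On a tie the scheduled draw is kept.

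**Enumeration of one later repeat in the same window**

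| Scheduled draw | Possible later days | Number | Repeat kept | Repeat left out |
|---|---|---|---|---|
| p − 1 | p to p + 3 | 4 | 1 (on day p) | 3 |
| p | p + 1 to p + 3 | 3 | 0 | 3 |
| p + 1 | p + 2 to p + 3 | 2 | 0 | 2 |
| Total | | 9 | 1 | 8 |

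Over eight windows: 8 × 9 = 72 positions, of which 8 × 8 = 64 leave the repeat out; 64/72 = 88.9%. A same-day repeat is a tie and is also left out.

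The first week shows the same thing. With Visit 3 drawn on Day 7, 8 or 9, the scheduled draw is at most one day from Day 8. An unscheduled draw on Days 2 to 6 is two to six days away, so it is never selected.

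**Direction.** The selected values are a subset of all post-baseline draws. The worst of the subset cannot exceed the worst of the whole set, so the most extreme shift shown can be understated but not overstated. For a single visit the rule can act either way. An unscheduled draw nearer the planned day can also displace a worse scheduled value.

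**Does the rule reach the shift tables?** SAP 16.5 expressly maps unscheduled ECGs through SAP 9.3, so the rule is meant to reach unscheduled safety data. SAP 16.2 defines the slit-lamp shift as going to all observations at later visits. SAP 16.4 has no such wording for laboratory data. The general rule therefore applies by default, but this is inferred and not stated.

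**What is left uncovered**

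| Unscheduled peak value | Listing | AE or AESI table | Laboratory table |
|---|---|---|---|
| Judged clinically significant | Yes | Yes, as an event with its grade | Only if selected by date |
| Meets combined hepatic AESI | Yes | Yes, Table 14.3.5 | Only if selected by date |
| Neither | Yes | No | Only if selected by date |

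The gap is the last row. Whether a value falls there depends on investigator judgement, for which the documents give no numeric limit.

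**The case against.** **A reader might infer that liver injury could vanish from the tables.** Protocol 17.1.2.6 does say "Initiate close observation of subjects by repeat testing of ALT, AST, and total bilirubin", at least weekly. However, Protocol 17.1.1 ties that work-up to alterations that already form the protocol-specified AESI. Such a subject is reported in an expedited manner and counted in Table 14.3.5, whichever draw is selected. Laboratory visits are also already weekly up to Visit 10, so the repeat testing need not create extra draws in that period. The documents do not support this reading.

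**A reader might infer that the rule removes extreme values.** It selects on date, not on result. If the abnormal result that prompted the repeat was the scheduled draw, that draw is usually kept and the repeat left out, even when the repeat is normal. Nothing in the documents shows that repeats tend to be worse. An elevation that persists to the next weekly visit would normally enter that visit's summary.

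**A reader might put a size on it as one lost case in 30.** That would turn 1/30 (3.3%, exact 95% CI 0.1% to 17.2%) into 0/30 (upper limit 11.6%). This is binomial arithmetic for a hypothetical case. The documents give no basis for expecting one.

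It can also be said that the secondary endpoint is AE incidence, seriousness and severity, that the safety analysis is descriptive, and that listings for about 30 subjects can be read in full. All of this stands, and it makes the point minor. It does not close the gap. The AE route depends on judgement and tabulates an event instead of the value, the AESI route needs two criteria in one sample, and the basis of the shift tables is still unstated.

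**Conclusion.** The point holds within narrow limits. For an unscheduled peak that is neither judged clinically significant nor a combined hepatic AESI, the plan as written provides a listing entry and, in most day combinations, no entry in any laboratory summary or shift table.

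This rests on three assumptions: that SAP 9.3 governs the laboratory shift tables by default, that the scheduled draw takes place within ±1 day, and that the repeat falls later in the same window. The 64 of 72 figure describes day combinations under the last two assumptions. No rate can be given, because the documents do not say how many unscheduled draws to expect or how they would be judged.

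Severity is minor. This is a gap in how safety data are presented, with no effect on the primary BCVA analysis or the sample size.

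**What to change.** 1. Keep the SAP 9.3 nearest-visit rule for by-visit laboratory summaries.
2. State in SAP 16.4 that Tables 14.3.10.1.2, 14.3.10.2.2 and 14.3.10.3.2 include a shift from baseline to the worst post-baseline value over all scheduled and unscheduled draws. Say for each analyte whether worst means high, low or both.
3. Add counts of subjects who at any post-baseline draw reach AST or ALT at least 3 times ULN, or total bilirubin at least 2 times ULN. These are the limits already in the AESI definition.
4. Add the count meeting both in one sample, as a cross-check on the hepatic entries in Table 14.3.5. The two can differ legitimately, because the AESI is limited to subjects with normal liver function at baseline.

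The cost is a few lines of SAP text and a little more programming on data already collected. The tables may look slightly less favourable. No visit, test or clinical procedure changes.

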9.4 Data Analysis Conventions

Quantitative variables will be summarized using descriptive statistics including the number of observations (n), mean, standard deviation (SD), median, minimum, and maximum values. Means, medians, and confidence intervals (CI) will be reported to two decimal places and SDs to three. Summaries for discrete variables will include frequency counts and percentages. All percentages will be rounded to one decimal place (i.e., XX.X%). Change from baseline will be calculated as the value at follow-up visit minus baseline.

The primary efficacy analysis will be evaluated at a two-sided significance level of 0.20. All p-values will be rounded to four decimal places; p-values less than 0.0001 will be presented as "<0.0001"; p-values greater than 0.9999 will be presented as ">0.9999".

9.5 Adjustments for Multiplicity

There will be no adjustments for multiplicity for this early phase, exploratory study.

10. Disposition of Subjects

Subject disposition will be presented in terms of the numbers and percentages of subjects who were enrolled, treated, completed the study, and discontinued from the study.

The number and percentage of subjects discontinued from the study and the reasons for study discontinuation will be summarized for all enrolled subjects. The reasons for study discontinuation that will be summarized include: AEs, treatment with prohibited concomitant medications, subject non-compliance, withdrawal of consent, pregnancy, termination of study, and other. A subject listing will be provided that includes the date (and study day) of and reason for premature study discontinuation.

The number and percentage of subjects with protocol deviations will be summarized for the ITT set. A subject listing will be provided that includes the date of the deviation and the deviation description.

Subject listings will be provided to list out informed consent dates, inclusion and exclusion criteria violations, and exclusions from the PP set.

11. Demographic and Baseline

11.1 Demographic and Vital Signs

Demographic variables collected in this study include age in years (at time of screening), sex, race, ethnicity, body mass index (BMI), weight, height, iris color, and study eye (OD or OS). Subjects who record more than one race will be grouped into a single category denoted as 'Multiple Race'.

Age (years) will be summarized using continuous descriptive statistics. Age will also be categorized as follows: <65 years and \geq 65 years.

The number and percentage of subjects will be presented for age category, sex, race, ethnicity, iris color and study eye (OD or OS). Percentages will be based on the total number of subjects in the ITTset. A subject listing that includes all demographic variables will be provided.

11.2 Baseline Characteristics

Baseline BCVA letter score as measured by the ETDRS testing method; CST, presence and height of IRF, SRF, and PED as measured by SD-OCT; and presence and size of CNV and leakage from CNV as measured by FP/FA will be included in the relevant summaries (including the demography summary) and listings.

12. Medical History and Concomitant Medications

12.1 Medical History

Medical history will be summarized using discrete summary statistics and presented at the subject level by system organ class (SOC) and preferred term (PT). If a subject reports the same PT multiple times within the same SOC, that PT will only be counted once within that SOC. As with the PT, if a subject reports multiple conditions within the same SOC, the SOC will only be counted once. Separate tables will be created for ocular and non-ocular medical history. Medical history will be coded using MedDRA, Version 21.0. The summaries will be based on the ITT set.

Listings of relevant medical history, including prior medical history within three months prior to Visit 1 (Screening) will be captured in the appropriate eCRF. A subject listing of reported medical history with start and stop dates (or ongoing) will be provided.

12.2 Prior and Concomitant Medications/Treatments

At the screening Visit 1 (Day -7 to Day -2), subjects will be asked what medications they are taking, as well as those the subject may have taken prior to screening. At each subsequent study visit, subjects

will be asked what concomitant medications they are currently taking or if there have been any changes to their medication since the previous visit.

All prior and concomitant ocular and non-ocular medications will be listed using the ITT set including generic name, route of administration, start date, stop date, dosage, and indication. Prior and concomitant medications will be categorized by WHO Drug Dictionary (B3 Global March 2018 or higher) classification for therapeutic class and drug name.

Counts and percentages of ocular and non-ocular concomitant medications will be summarized separately, and summaries will be displayed for the ITT set. Subjects with multiple medications in the same WHO drug dictionary class or preferred name will be counted only once for that respective WHO drug dictionary class or preferred name.

13. Dosing Compliance and Treatment Exposure

13.1 Dosing Compliance

A dose is considered a single 400 mg tablet. Subjects are instructed per protocol to administer a dose twice daily (i.e., once in the morning and once in the evening). Dosing compliance (% compliance) will be assessed by calculating the number of actual doses received and comparing that to the number of expected doses as follows:

$$\text{Compliance (\%)} = \frac{\text{Number of Actual Doses Received}}{\text{Number of Expected Doses}} \times 100$$

The number of actual doses received will be calculated from the the number of dispensed and returned tablets as recorded in the eCRF. The number of expected doses that will be used for calculating compliance will be calculated as {2x [date of last dose – date of first dose]} +1 for all subjects, regardless of study completion status. Overall compliance will also be categorized as compliant (≥75%) and non-compliant (<75%).

Treatment compliance (%) will be summarized for the Safety set using continuous descriptive statistics. The compliance categories defined above will be summarized with counts and percentages.

A subject listing of compliance will also be produced.

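### The expected-dose formula in SAP 13.1 is one dose short when treatment ends on an evening dose: a small counting error, to be corrected and the measure labelled as on-treatment compliance

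*SAP*

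**What the plan says.** SAP 13.1 fixes the unit ("A dose is considered a single 400 mg tablet") and the regimen: subjects are to "administer a dose twice daily (i.e., once in the morning and once in the evening"). The numerator comes from "the number of dispensed and returned tablets as recorded in the eCRF". The denominator is "2x [date of last dose – date of first dose]} +1 for all subjects, regardless of study completion status", preceded in the text by an opening brace.

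Three outputs follow. On the percentage itself: "Treatment compliance (%) will be summarized for the Safety set using continuous descriptive statistics". On the two classes: "Overall compliance will also be categorized as compliant (≥75%) and non-compliant (<75"%). By subject: "A subject listing of compliance will also be produced".

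SAP 13.2 separately summarizes days of exposure and total doses received. SAP 10 summarizes discontinuations with reasons. The Evaluable and Per Protocol definitions (SAP 8.3 and 8.4) do not mention the 75% cut-off.

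On the final dose, the schedule tables (Protocol 15.1, SAP 4.2) and their footnote 4 show supervised dosing at Visits 2 to 8. The sampling table in Protocol 17.2.1 times the Visit 8 sample relative to a dose. The Visit 8 procedure list in Protocol 8.2.3.1 includes no dose.

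**The concern.** With two doses a day, the number due between two dates depends on whether the first and last days each carried one dose or two. The SAP uses one constant, +1, for everyone. That fits a subject who takes two doses on Day 1 and ends on a clinic dose. It does not fit one whose last tablet was taken in the evening, for example a subject withdrawn at a visit before that day's clinic dose. That subject has one more dose due than the formula allows, and perfect intake is reported as more than 100%.

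At stake is the accuracy of Table 14.1.5 (compliance). Values slightly above 100% would look like overuse or lost tablets when they are only a counting error. The table's title also does not say that the measure covers only the time up to the last dose taken.

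**Working it through.** **Inputs.** One tablet per dose and two doses a day (SAP 13.1). Visit 2 is Day 1 and Visit 8 is Day 43 (SAP 4.2). The cut-off is 75% (SAP 13.1). Planned enrolment is 30, with about 25 evaluable (SAP 6). Assumption: a clinic dose is the first of that day's two doses. The documents do not give the clock time of the first dose.

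**Planned course.** The SAP states a formula but no expected count. Let d = last dose date − first dose date, so the formula is 2d + 1. For Day 1 to Day 43, d = 42 and the formula gives 2 × 42 + 1 = 85. Direct count: 2 doses on each of Days 1 to 42 is 84, plus one on Day 43 is 85. They agree.

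**Direct count in the four possible cases.**

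| Day 1 | Last day | Doses due | Formula 2d + 1 |
|---|---|---|---|
| two doses | morning or clinic dose last | 2d + 1 | exact |
| two doses | evening dose last | 2d + 2 | one short |
| one (evening) dose | evening dose last | 2d + 1 | exact |
| one (evening) dose | morning dose last | 2d | one too many |

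**Full adherence, two doses on Day 1, evening dose last.**

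| Last-dose day | Due | Formula | Reported compliance |
|---|---|---|---|
| 1 | 2 | 1 | 200% |
| 2 | 4 | 3 | 133.3% |
| 8 | 16 | 15 | 106.7% |
| 22 | 44 | 43 | 102.3% |
| 42 | 84 | 83 | 101.2% |
| 43 | 86 | 85 | 101.2% |

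**Effect on the 75% class.** For last-dose day D, the formula gives 2D − 1 and the correct count is 2D. A subject with a tablets is moved into the compliant class only if a/(2D − 1) ≥ 0.75 and a/(2D) < 0.75, that is 1.5D − 0.75 ≤ a < 1.5D. If D is even, no whole number fits. If D is odd, exactly one does: a = 1.5D − 0.5. Examples: Day 43 with 64 tablets, 64/85 = 75.3% against 64/86 = 74.4%; Day 21 with 31 tablets, 31/41 = 75.6% against 31/42 = 73.8%.

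**Effect on the mean of 30 subjects.** One fully adherent Day 8 evening stopper adds 6.7/30 = 0.22 points; one Day 22 evening stopper adds 2.3/30 = 0.08. If 25 subjects complete at 100% and 5 stop after the Day 8 evening dose, the mean is (25 × 100 + 5 × 106.7)/30 = 101.1%.

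**Visit 8.** If no dose is taken at Visit 8, a completer on the nominal schedule ends on the Day 42 evening dose. Then 84 doses are due, the formula gives 2 × 41 + 1 = 83, and every fully adherent completer of this kind reads 84/83 = 101.2%.

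**Early stopping.** A subject whose last dose is the Day 22 morning dose has 43 due, by the formula and by direct count. Taking 32 gives 32/43 = 74.4%, non-compliant; taking 33 gives 76.7%, compliant.

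**The case against.** The strongest reply is that the formula is exact for the course as scheduled, the error is a single tablet, and the figure is purely descriptive. All of that stands, and it is why the point is minor. It does not make the formula right for evening-dose stoppers, to whom the SAP expressly applies it.

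A second reply is that stopping the denominator at the last dose taken is an ordinary way to measure adherence while on drug, and that the SAP says openly that it does so. That also stands. It calls for a label, not a different measure.

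A reader might infer something stronger: that early stoppers and over-users are all reported as compliant, and that Table 14.1.5 is the only place where adherence can be judged. The documents do not support this.

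- Early stoppers who took less than 75% of the doses due before stopping are classed as non-compliant, as the 32/43 case shows.
- A subject above 100% does fall in the compliant class, because there is no upper limit. But compliance is also summarized as a continuous variable, with its maximum (SAP 9.4), and listed by subject.
- Early stopping is visible in Table 14.1.6 (exposure), in total doses received and in the disposition summary.
- The +1 does not cause either pattern. They come from the on-treatment denominator and the two-class split.

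Unreturned tablets do count as taken under a dispensed-minus-returned rule. How far this could raise the figure cannot be said, because the bottle contents in Protocol 6.1.2 are redacted, and Protocol 6.2 requires sites to verify that unused study agent has been returned.

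**Conclusion.** The expected-dose formula is wrong by one dose for a definable group: subjects with two doses due on Day 1 whose last dose was an evening dose. For full adherence the excess is about 1 to 2 points after three weeks or more of treatment, 6.7 points at Day 8, and large only in the first days. The 75% class changes at one tablet count per odd last-dose day and otherwise not at all. In the opposite case, a single dose on Day 1 and a morning dose last, the formula is one dose too high.

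These figures assume that the clinic dose is the day's first dose. The size for completers depends on an inconsistency between the documents: if there is no Visit 8 dose, the one-dose error would affect completers who end on the Day 42 evening dose, at 101.2% each. The BCVA analysis, the safety analyses and the analysis sets are unaffected. This is a minor correction, worth making because it is cheap.

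**What to change.** In SAP 13.1:

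1. Set expected doses to 2 × (last dose date − first dose date + 1). Subtract 1 if the last dose was the morning or clinic dose of that day, and subtract 1 if only one dose was due on Day 1. When first and last dose fall on the same date, subtract at most 1, so that a single dose counts as 1/1.
2. Apply the first subtraction at any visit. Limiting it to Visit 8 would create a new error: a subject ending on the Day 15 clinic dose was due 29 doses but would be assigned 30, and one who took only the supervised Day 1 dose would read 1/2 = 50%.
3. If the time of the last dose is not recorded for home doses, state the assumption used.
4. Call the measure on-treatment compliance in the text and in the title of Table 14.1.5.

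Separately, reconcile the schedule tables with the Visit 8 procedure list on whether a dose is taken at that visit, and make the expected count follow the answer.

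Two additions are optional: a third class above an upper limit chosen by the sponsor, and a rule that tablets from unreturned bottles are not counted as taken.

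The cost is a few sentences in the SAP and a few lines of code. Visits and the primary test do not change.
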